The researchers will deliver the Intervention with the patients participating in the study at leaving points, during the patient's journey through the COPD service, as specified in the diagram below. Patients enter the pulmonary rehabilitation (PR) section of the COPD service post-acute episode or by GP referral. Patients are then clinically assessed for suitability to continue in the exercise component of the service. If patients are deemed suitable for exercise then they continue onto PR. Post PR they have a review, 30 minutes with a clinician to ascertain their progress through the programme and to recommend continuation of exercise. At this point patients can also leave the programme.

Furthermore patients are offered maintenance exercise therapy – and are reviewed yearly, during these reviews other exercise and activity can also be recommended, patients can also leave the service at this point. These transition points in the care pathway; leaving the PR programme, or at

yearly maintenance review patients will be offered to participate in the GENIE study and provided with study information.

1. Those patients completing a PR programme, and in whom we wish to provide clear direction and signposting to appropriate social activity
2. Those who have benefitted from maintenance for 1 year or more, but at review could be encouraged to do more and have more social outlets.

Currently, patients leaving PR classes are usually offered the option to join the maintenance exercise class, delivered by the COPD team, other exercise options are considered, however, these options are currently limited or difficult to access in one place.

Building capacity to carry out the evaluation: Ensuring the GENIE database contains an appropriate library of social and health activities suitable for the Southampton COPD patient. The lead researcher will investigate existing exercise, social and community activities, then populate and categorise the GENIE database.

Introducing the intervention: In order to successfully implement the GENIE tool into clinical practice; the clinical team needs to be at the core of the process in order to ensure appropriate and effective facilitation. Therefore, the clinical team will be briefed as the study progresses, through question and answer sessions and direct learning opportunities in how the tool works and the objectives of the study.

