Selection and patient information: Patients in the COPD service; at the outset of their assessment, the end of PR and during maintenance sessions will be informed that the GENIE implementation evaluation is in progress.

Patients participating in these aspects of the service will be offered the opportunity to volunteer for the study, by the clinical team. If patients are interested they can then provide their names to the clinical staff to keep on a secure Solent database. Patient information sheets and invitation letters will be given out to the interested patients at their clinical visits to minimise postal and /or extra visits.

Once patients have received an information sheet, they will be allowed at least 72 hours to read and digest the information, (patient information sheets, consent and GP letters are separate documents), and share this with their friends and family if they wish to. Ideally, patients are provided with information in their clinical visits and are returning for clinical visits then appointments for research could be amalgamated with usual clinical visits. In this way extra study visits can be reduced. Patients, now participants, will be invited to consent and be randomised at the point of leaving usual clinical care. Furthermore, all patients at this point will have the opportunity to opt out of the study.

Once the participant is randomised (using block randomisation technique in clinic), then they will all receive normal clinical care (discharge planning with suggested activities), and the GENIE tool intervention, in the GENIE group, this is in addition to usual clinical care. Baseline questionnaires will also be administered at this visit.

The follow up period will commence 3 months (12 weeks) (+/- 1 week) from the day the GENIE tool was initially delivered. Participants will be invited back, via letter and /or phone call to attend their three month follow up visit at Bitterne Health Centre.

Solent NHS Trust will be the overall NHS organisation with one venue for study delivery; Bitterne Health Centre.

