Stage 3: This section will then link individuals to prioritised and valued activities and resources (links are to a pre-created database where local organisations and resources have been categorised).

Stage 4: The GENIE Tool then presents options in a user-friendly way, on a Google map with clear details about access, an example below:

Both groups will receive usual care, however one arm will have the addition of the intervention both will be called for a review at:

Three monthly follow up (+/- 1 week)

Six questionnaires will be administered. EQ-5D, health utilisation questionnaire, HEIQ and wellbeing questionnaires (CAT, GAD, PHQ-9), as well as the optional health behaviour questionnaire, so in 30 participants this will be seven, these will be repeated at 3 months post intervention (+/- 2 week). Furthermore, for those in the intervention arm, feedback and reflection discussions will be initiated using the network diagrams. Participants will be asked again for their permission to tape record these discussions to ensure parity and quality assurance between researchers.

Analysis of Outcomes

The study gathers data from the intervention arm and the non-intervention arm at baseline and 3 months post intervention. Results will be compared between the groups at baseline and 3 months post intervention. An economic analysis will be performed using a modified version of the Client Service Receipt Inventory (CSRI) (Beecham and Knapp 1999) Medication, health service use will be measured at baseline, 3 months post implementation and follow up. The modified version has been tailored to capture the needs of the target population (COPD patients). The CSRI has been widely used in previous research studies and has been evidenced as a valid measure of frequency of health service use (Patel 2005). The EQ5D is included to assess health status of patients during the GENIE intervention. Wellbeing score (CAT) and HEIQ and in the optional sub-group health behaviours (dietary intake, appetite, alcohol consumption and smoking habits) will be compared at baseline and 3 months. Furthermore, patient uptake of the social activities is to be recorded on paper using the Genie tool and compared between groups.

Rationale for the service implementation and evaluation design

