Following the training, the participants will be given the tools required to roll out the intervention

- Paper and web-based concentric circles with typologies and support suggestions
- Guidebook on how to deliver GENIE
- Access to the database and website

Identification, enrolment and randomisation

[figure not shown]

Table of Events

	Consent and Randomisation	Pre – intervention data collection	12 weeks post intervention data collection (+/- 1 week)	Potential 1 year follow up phase
Consent form discussion and taking informed consent	x			
Randomisation (Block)	x			
EQ-5D		X	x	x
Health Care Utilisation Questionnaire		X	x	x
Socio-economic background / demographic data		X		
Gender		X		
Disease severity (FEV1)		X		
HEIQ (Self-management)		X	x	
Optional Health behaviour questionnaire		x	x	x
CAT		X	x	x
Gad-7 /		X	x	
PHQ-9		x	x	x
Uptake discussion / online survey			x	x

Quality Assurance

The delivery of the intervention will be taped in as many cases as consented to ensure that the intervention is delivered consistently by the research team to all patients. The tape recording is for quality assurance, and is not intended for research utilisation or publication.

Future work

The participants included in this initial 3 months of the study could be followed up again in 1 year (12 months) to ascertain longer term outcomes and longevity of connections made. This element could consist of a paper or online survey to understand the uptake rates of the social actives 1 year on, and further investigation into QOL, **healthcare use and the option of assessing health behaviours.** All participants would be given the option of continuing for a year, and therefore those who continue would be decided by participant preference to remain in the study.

Analysis Plan

Primary Outcomes

Descriptive statistics of the cohort,

Descriptive statistics of the cohort will be reported including but not limited to; age, gender, severity of disease then the analysis will be broken down into 5 distinct sections;

- a) Pre and post intervention cost utility analysis for the usual care group and the intervention group.
- b) Comparative group - pre and post cost utility analysis; calculated cost per QALY (quality adjusted life years) gained and cost of healthcare usage per patient– usual care group at 3 months after leaving the COPD service compared with the post intervention group 3 (+/- 1 week) months after leaving the COPD service, with significance.

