(English) EQ-5D-5L Pdf

Health care utilisation questionnaire

Healthcare Usage Questionnaire

We would like to know how much use you have made of the health and social services over the last 3 months. If you are not exactly sure, we would rather have your best guess than no information at all.

Please answer every question, even if the answer is 'No'.

1) Over the last 3 months, if, and how many times, have you used any of the following:

Type of Service	No	Yes	If yes: Number of visits
GP		At home	
		In the surgery	
		On the phone	
Practice nurse		At home	
		In the surgery	
		On the phone	
Social worker		At home	
		In the facility	
		On the phone	
Visit at home from a community nurse or Dr			
Specialist community clinic –with consultant			
NHS Smoking Cessation clinic			
Other (describe)			

2) Hospital outpatient visit for breathing related issues

Episode*	Name of the hospital	Reason for appointment	Specialty of Department	Number of appointment*
1 st				
2 nd				
3 rd				
4 th				

*Episode means a visit or group of visits related to a particular problem. Please write down how many appointments you have had for each episode

3) Accident and Emergency for COPD / breathing issues

Episode	Name of the hospital	Reason for visit	Referral from
1 st			GP
			Outpatient
			Self-referral
2 nd			GP
			Outpatient
			Self-referral
3 rd			GP
			Outpatient
			Self-referral
4 th			GP
			Outpatient
			Self-referral

4) Hospital Inpatient for COPD / breathing and chest issues

Episode	Name of hospital	Ward Speciality	Reason for admission	No of nights*
1 st				
2 nd				
3 rd				
4 th				

*If you were treated as a day patient (day case), then please write 0 under "number of night"

5) Are you currently in paid employment?

No (please go to question 5b) Yes (please go to question 5a)

5a If yes, how many days have you been absent from work because of COPD in the last 3 months?
Please state how many days 5b If you are not employed:,

In the last 3 months have you had to stop work completely due to your COPD disease

No

Yes

6) Over the last 3 months has a relative or friend taken time off work to look after you?

No

Yes, how many days

7) In the last 3 months, approximately how much additional money have you spent on travel (taxi car park fees and public transportation because of your COPD disease)

None

Yes, I spent £ _____

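### Item a) asks for a within-arm pre/post cost-utility result, but no EQ-5D exists for the start of the pre period, and costs can fall in both arms without any GENIE effect

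*Combined protocol and SAP*

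**What the plan says.** **The analysis.** In the Analysis Plan, under Primary Outcomes, item a) reads "Pre and post intervention cost utility analysis for the usual care group and the intervention group". Item b) is the comparison of the two groups at 3 months. The request for "calculated cost per QALY (quality adjusted life years) gained and cost of healthcare usage per patient", and for significance, appears in item b). Item a) itself gives no formula, ratio or test.

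**When utility is measured.** Analysis of Outcomes states: "The study gathers data from the intervention arm and the non-intervention arm at baseline and 3 months post intervention". Under Implementation Design, participants "will be invited to consent and be randomised at the point of leaving usual clinical care", and the protocol adds: "Baseline questionnaires will also be administered at this visit". The Table of Events agrees: EQ-5D and the utilisation form are given before the intervention, at 12 weeks, and possibly at 1 year. No EQ-5D is taken before the baseline visit.

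**Which period the costs cover.** The Healthcare Usage Questionnaire in the Appendices asks "how much use you have made of the health and social services over the last 3 months". The baseline form therefore covers month -3 to month 0.

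**Who is recruited.** Implementation Design says: "Patients enter the pulmonary rehabilitation (PR) section of the COPD service post-acute episode or by GP referral". The Population section puts the post-rehabilitation review after a course of usually 12 sessions. Patients with a year or more of maintenance exercise are also eligible, and the protocol says the mix of the two streams cannot be forecast. The questionnaire has sections for A&E, inpatient and outpatient care, but no row for rehabilitation or maintenance classes.

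**The concern.** A cost-utility analysis needs costs and QALYs over the same period. For the pre period, the plan collects three months of costs but only one utility value, at the end of those months. The QALY half of item a) is therefore not identified by the data, and the plan states no rule for filling the gap.

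The cost half can be computed, but it is an uncontrolled before/after comparison. Some patients reach baseline soon after an acute episode, and the form records the hospital care that goes with one. Where that care falls in the recall window, cost will be lower afterwards if the patient simply recovers.

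This matters because of how the result may be used. Risks / benefits makes wider use of the tool depend on benefit observed among intervention-arm participants. Ethical Considerations describes the trial as a way to learn about time and cost before full implementation. A within-arm saving, listed among the primary analyses, could be taken as evidence for that decision.

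**Working it through.** The plan gives no figure for item a), so there is nothing to reproduce. Its only design figure, 30 to 60 patients per group, does not enter this check.

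**1. QALYs**

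Let u(-3), u(0) and u(3) be the mean utility three months before baseline, at baseline and at the 3-month visit. The documents provide u(0) and u(3) only. I take each window as 0.25 year, since the protocol equates 3 months with 12 weeks, and use the area under the curve:

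- Pre QALYs = 0.25 x [u(-3) + u(0)] / 2 = 0.125 x [u(-3) + u(0)]
- Post QALYs = 0.25 x [u(0) + u(3)] / 2 = 0.125 x [u(0) + u(3)]
- Post minus pre = 0.125 x [u(3) - u(-3)]

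The baseline value cancels, and the answer depends on the value that is not collected. Suppose nothing changes after baseline, so u(3) = u(0), and let d = u(0) - u(-3) be the unmeasured earlier change. The values of d are assumptions.

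| d | Apparent QALY change, 0.125 x d |
|---|---|
| -0.05 | -0.00625 |
| 0 | 0 |
| +0.05 | +0.00625 |
| +0.10 | +0.0125 |
| +0.15 | +0.01875 |

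The shift is the same in either arm. Carrying the baseline value back sets d = 0. That can be computed, but it is an assumption the plan does not state. By contrast, QALYs over the three months after baseline need only u(0) and u(3).

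**2. What can lie in the cost window**

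Three months is about 13 weeks. The number of sessions per week is not stated. At an assumed one or two per week, 12 sessions take 12 or 6 weeks, which leaves about 1 or 7 weeks of the window before the course began. For a patient reviewed promptly, the course falls within the window, while a preceding acute episode may or may not. Patients referred by their GP, or with a year or more of maintenance, need not have had a recent acute episode.

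**3. Possible cost fall with no GENIE effect**

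None of the inputs here is in the documents. Assume 20-40% are admitted in the pre window, 10-15% in the post window, and £1,500-£3,000 per admission:

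- Fall per patient = (pre share - post share) x cost per admission
- Lowest: (0.20 - 0.15) x £1,500 = £75
- Highest: (0.40 - 0.10) x £3,000 = £900

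A second set of assumptions (10-30% with a £1,000 episode, of which 50-100% do not recur) gives 0.10 x 0.50 x £1,000 = £50 to 0.30 x 1.00 x £1,000 = £300. The direction is the same, but the size depends on the assumptions.

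Rehabilitation sessions add nothing unless they are costed. If they were, at an assumed £20-£60 per session with 25-100% of participants being rehabilitation leavers, the fall when the course ends would be 12 x £20 x 0.25 = £60 to 12 x £60 x 1.00 = £720 per patient.

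**4. Between arms**

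Randomisation takes place at the end of the pre window, so both arms share these influences. Their expected contribution to the difference between arms is zero.

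**The case against.** The strongest defence is that item a) does little harm. It reports both arms, so a fall due to recovery would also appear under usual care. The primary objective is comparative, item b) is the randomised comparison, and the plan does not rank its listed analyses. Item a) prescribes no ratio and no test. Cost change, utility change and post-baseline QALYs can all be computed by arm, and a pre-period QALY becomes computable once baseline utility is carried back.

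Most of this stands, and it limits the point to item a). It does not remove the point. A cost-utility analysis by name combines cost with QALYs, and the pre-period QALY still rests on an assumption that the plan does not make. The fall in usual care protects the reader only if conclusions are confined to the difference between arms, and the plan does not say so.

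Three stronger readings are tempting, and the documents do not support them:

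- **That the baseline costs include the rehabilitation course.** The form has no row for it. It could enter only as a free-text entry under other services, or from a cost source the plan does not mention. It is also not recent for patients with a year or more of maintenance.
- **That costs will fall because the window holds the acute care that led to rehabilitation.** Entry may be by GP referral, maintenance patients are recruited too, and a course of about 12 weeks would push most earlier episodes out of the window. Costs can fall; the documents do not show that they will.
- **That the economic evaluation as a whole fails.** Item b), taken over the period after randomisation, is computable and free of this bias in expectation.

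**Conclusion.** The concern holds for item a) only. Its QALY component is not identified without an assumed utility at month -3. For unmeasured changes of 0.05 to 0.15, the within-arm result moves by about 0.006 to 0.019 QALY in either arm with no change after baseline. Its cost component can show a fall with no GENIE effect, arising in some rehabilitation leavers only. The documents do not establish the size of that fall; £75 to £900 per patient follows from assumed admission shares and costs and is illustrative. The plan should be changed, because item a) as written would give a within-arm economic result that is not identified and is open to confounding by recovery.

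**What to change.** - Present item a) only as a descriptive table of 3-month cost and EQ-5D by arm at baseline and 12 weeks, with no within-arm cost-per-QALY ratio and no test.
- State that all economic conclusions come from the comparison between arms over the 12 weeks after randomisation, with QALYs by area under the curve adjusted for baseline EQ-5D, and costs adjusted for baseline 3-month cost. Item b) also carries pre and post in its title, so it should be tied to this window explicitly.
- State whether rehabilitation and maintenance sessions are costed and, if so, from what source.

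The first two changes take a few lines in the Analysis Plan and need no new data. The third is a statement, unless the sponsor chooses to cost the sessions. The downside is that a within-arm savings figure is no longer reported.

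### The between-arm cost-utility comparison does not say how baseline EQ-5D and baseline cost enter; regression adjustment for both would be more precise at almost no cost

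*Combined protocol and SAP*

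**What the plan says.** Under Analysis Plan, Primary Outcomes, item a) is "Pre and post intervention cost utility analysis for the usual care group and the intervention group". Item b) is headed "Comparative group - pre and post cost utility analysis". It asks for "calculated cost per QALY (quality adjusted life years) gained and cost of healthcare usage per patient", and its contrast is the "usual care group at 3 months after leaving the COPD service compared with the post intervention group" at the same time point, with significance to be reported.

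The section Analysis of Outcomes adds, for all results, "Results will be compared between the groups at baseline and 3 months post intervention". It describes EQ-5D as a measure of health status and says the economic analysis uses a modified service-receipt inventory.

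The Table of Events schedules EQ-5D and the health care utilisation questionnaire before the intervention and again at 12 weeks. The paragraph on initial data collection confirms that both arms complete them. The questionnaire in the Appendices looks back 3 months, so the baseline form gives each participant a cost for the 3 months before entry. Recruitment is 30 to 60 per arm.

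Nowhere is there a QALY formula, an EQ-5D-5L value set, a covariate adjustment, or a rule for using baseline EQ-5D or baseline cost in item b). A test is named only for items c) and d).

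**The concern.** Item b) can be carried out in more than one way on the same data. Its heading and its talk of QALYs gained point to change from baseline. Its contrast clause can be read as 3-month values only. The ordinary meaning of a QALY suggests an area under the curve, which without adjustment gives the baseline value half the weight.

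At 30-60 per arm, a chance baseline difference in EQ-5D can be as large as a plausible treatment effect. The 3-month-only and unadjusted-area readings pass that difference into the QALY result. The same ambiguity applies to cost.

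Cost effectiveness is in the trial's title, and items a) and b) stand under Primary Outcomes. If the method is left open, it can be settled after the data are seen, and two of the possible choices give up precision that the collected baselines would supply.

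**Working it through.** The plan states no QALY figure, SD, effect size or power, so there is nothing of its own to reproduce.

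**Inputs from the documents.** Follow-up is 12 weeks, T = 12/52 = 0.2308 year; n = 30 or 60 per arm; allocation is 1:1.

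**Assumptions, not in the documents.** EQ-5D SD 0.20, 0.25 or 0.30 at both times; baseline to 3-month correlation r = 0.6, 0.7 or 0.8; linear path between visits; true 3-month gain 0.05, with 0.03 and 0.10 as alternatives; normal arm differences.

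**Readings.** Let d0 and d1 be the arm differences (GENIE minus usual care) at baseline and 3 months. Given d0, the expected d1 is gain + r·d0. Apart from the factor T/2, which does not affect the sign:

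| Reading | Estimate | Weight left on d0 | SE ÷ (SD·√(2/n)) |
|---|---|---|---|
| Unadjusted area | d0 + d1 | 1 + r | √(2+2r) |
| 3-month only | d1 | r | 1 |
| Change score | d1 − d0 | −(1 − r) | √(2−2r) |
| Baseline-adjusted | d1 − r·d0 | 0 | √(1−r²) |

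Unadjusted area and change score take opposite signs whenever |d0| > |d1|; this needs no assumption. The change score over-corrects for baseline by a smaller amount than the other two readings leave in.

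**Illustration (assumed means).** GENIE goes from 0.60 to 0.65 and usual care from 0.65 to 0.66, so d0 = −0.05 and d1 = −0.01.
- Unadjusted area: 0.2308 × (−0.06)/2 = −0.0069 QALYs.
- 3-month only, credited over the full interval: 0.2308 × (−0.01) = −0.0023.
- Change score: 0.2308 × 0.04/2 = +0.0046.
- Adjusted, slope 0.6: 0.2308 × (−0.01 + 0.03)/2 = +0.0023.

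For cost, suppose GENIE goes from £400 to £420 and usual care from £500 to £450. The 3-month difference is −£30; the difference in change is +£70.

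**Central case** (SD 0.25, r = 0.7, gain 0.05). The true QALY gain is 0.05 × 0.2308/2 = 0.00577. The chance of a wrong sign is Φ(−0.00577/SE).

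| Reading | SE, n=30 | Wrong sign | SE, n=60 | Wrong sign |
|---|---|---|---|---|
| Unadjusted area | 0.01373 | 33.7% | 0.00971 | 27.6% |
| 3-month only* | 0.00745 | 21.9% | 0.00527 | 13.7% |
| Change score | 0.00577 | 15.9% | 0.00408 | 7.9% |
| Adjusted | 0.00532 | 13.9% | 0.00376 | 6.3% |

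*On the T/2 scale. Crediting the full interval doubles both the SE and the gain and leaves the sign results unchanged.

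**Wrong sign over the full grid, n=30 / n=60.**

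| Reading | Gain 0.03 | Gain 0.05 | Gain 0.10 |
|---|---|---|---|
| Unadjusted area | 37-42% / 32-39% | 29-37% / 22-32% | 14-25% / 6-17% |
| 3-month only | 28-35% / 21-29% | 17-26% / 9-18% | 3-10% / at most 3% |
| Change score | 18-33% / 10-27% | 6-24% / 2-15% | at most 7% / 2% |
| Adjusted | 17-31% / 9-25% | 5-21% / 1-13% | at most 5% / 1% |

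**Opposite signs on the same data, n=30 / n=60** (from the joint normal distribution of the two readings).
- Change score against unadjusted area: about 42-47% / 37-44% at gain 0.03, 33-43% / 24-36% at 0.05, 15-28% / 6-17% at 0.10.
- Change score against 3-month only, gain 0.05: 18-28% / 9-21%.
- Change score against adjusted, gain 0.05: 3-11% / 1-8%.

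**Precision gained.** The ratio of adjusted to change-score SE is √((1+r)/2), which is 0.89 to 0.95, a saving of 5-11%. Against 3-month only it is √(1−r²), 0.80 to 0.60, a saving of 20-40% on the T/2 scale. Against unadjusted area it is √((1−r)/2), 0.45 to 0.32, a saving of 55-68%.

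**What remains after adjustment.** In the central case the expected 95% interval is 0.00577 ± 1.96 × 0.00532, or −0.005 to 0.016, at n=30, and −0.002 to 0.013 at n=60. Over the grid, power at gain 0.05 is 13-36% / 21-63%.

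**The case against.** The strongest reply is that the plan does bring the baseline in. Item b) is headed as a pre and post analysis and speaks of QALYs gained. The 3-month-only reading has to set that heading aside and lean on a general sentence about all results, and no section words an area under the curve. If a change score is meant, it seldom disagrees in sign with the adjusted estimate, and the largest disagreement figures do not apply. This stands as to size: the readings are not equally likely. It does not remove the gap, because the same item goes on to compare the arms at 3 months and gives no formula.

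A second reply is that much of the trouble is small sample size. That also stands. Adjusted estimates still have the wrong sign in 5-21% of trials at 30 per arm and gain 0.05, and with intervals reported many sign differences would not alter a conclusion. It is no reason to forgo precision that costs nothing.

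A reader might also infer that the plan will put a p-value on the cost-per-QALY ratio, or draw a cost-effectiveness conclusion from item a) within each arm. The text does not establish either. The request for significance may concern cost per patient only, and item a) may be meant descriptively. Both need clarifying; neither is a demonstrated error.

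**Conclusion.** The point holds as a prespecification gap with a better method available: how baseline EQ-5D and baseline cost enter item b) is unspecified, and each reading that the wording allows is less precise than a baseline-adjusted estimate. That ranking holds for any correlation strictly between 0 and 1 under the equal-variance model above, with the 3-month-only reading taken on the T/2 scale. The percentages depend on the assumed SD, correlation and gain.

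The size depends on the reading. If change from baseline is intended, as the wording suggests, adjustment saves 5-11% of the standard error and changes the sign in 3-11% of trials at 30 per arm and 1-8% at 60 (gain 0.05). If a 3-month-only or unadjusted-area analysis were done, the loss would be much larger.

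Two stronger conclusions are tempting. One is that the plan ignores baseline altogether; item b)'s heading contradicts that. The other is that the sign of the QALY result is close to a coin toss under the plan as written. The 33-43% figure needs the unadjusted-area reading, which the wording supports least, and it falls to 15-28% at a gain of 0.10. This should be fixed before analysis, but it does not undermine the design.

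**What to change.** Make item b) the economic comparison and prespecify the following:
- QALYs as the area under the EQ-5D curve over follow-up, with the EQ-5D-5L value set named.
- Incremental QALYs by randomised arm from a regression that includes baseline EQ-5D.
- Incremental cost by randomised arm from a regression that includes baseline 3-month cost, stating which questionnaire items count as cost. The form also collects work absence, carers' time, travel and other private spending.
- Both reported with bootstrap intervals, on the cost-effectiveness plane or as net benefit at stated thresholds. No p-value on the cost-per-QALY ratio; say which quantity the request for significance covers.
- Item a) as a description of costs and EQ-5D before and after in each arm.

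The cost is a few lines of analysis-plan text and modest extra analysis of data already scheduled. No new data are needed. The result will still be imprecise at 30-60 per arm and should be reported as an interval, not a verdict.

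The plan's statement "Baseline questionnaires will also be administered at this visit" does not fix whether they are completed before the participant learns the allocation. That is a matter of conduct and should be raised as a separate point.
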